8.2.3.1.4. Safety specifications

For the safety specifications shown in Section 6.1, the number and proportion of patients will be tabulated. The number and proportion of patients with safety specifications will be tabulated by SOC and PT for each action taken and outcome.

In addition, safety specifications will be analyzed, taking into account the difference in exposure period, as described in Section 8.1.4.

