## 6. RATIONALE AND BACKGROUND

VynDAQel obtained the marketing authorization for the indication of “suppression of progression of peripheral neuropathy in transthyretin-type familial amyloid polyneuropathy” in September 2013. After an additional application for the indication of “transthyretin amyloid cardiomyopathy (hereinafter referred to as ATTR-CM)” was filed in November 2018, the approval for the additional application was obtained in March 2019.

VynDAQel is an orally available low molecular weight compound that binds to the thyroxine binding site of TTR and specifically stabilizes the TTR tetramers in plasma for both genetic variants and wild-type. This mechanism of action is expected to inhibit dissociation of the tetramers into monomers, which is a rate-limiting step in amyloid formation, suppress amyloid deposition in tissues such as the myocardium, and delay or deter the progression of ATTR-CM disease.

“VynDAQel Capsules Special Investigation - Investigation on patients with transthyretin amyloid cardiomyopathy -” (hereinafter referred to as this study) will be conducted to

*PFIZER CONFIDENTIAL*

*CT24-WI-JPN-GPSP01-RF09 7.0 Non-Interventional Study Protocol Template for Secondary Data Collection*

*Study 15-Sep-2022*

*Page 9 of 39*

comprehend information on the safety (e.g., onset status of adverse reactions), etc. of patients who are treated with Vyndaqel for the treatment of ATTR-CM.

Vynmac was approved for marketing in September 2021 for ATTR-CM because it demonstrated the same safety and tolerability as those of tafamidis meglumine 80 mg (20 mg x 4 capsules) containing the same physiologically active ingredient in patients with ATTR-CM. In this study, Vynmac is also investigated: when Vynmac is used during the observation period, observation will be also continued until the planned observation period is completed to comprehend information on the safety (e.g., onset status of adverse reactions), etc. of Vynmac.

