**8.2.4. Planned study period**

The planned period covered by this study is as follows.

Investigation period: March 2019 to September 2023 (From the start date of observation for the first subject to the end date of observation period for the last subject)

Registration period: March 2019 to March 2021 (From the start date of administration for the first subject to the start date of administration for the last subject)

However, CRFs may be collected when additional information needs to be collected.

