#### **8.2.6. Observation period**

[figure not shown]
30 months (Week 130) from the start of administration (Day 1)

However, for patients who discontinued this drug during the observation period, the observation period will be until the first visit after the date of discontinuation.

[figure not shown]
In this study, information will be collected using a booklet type CRF. Information during the following periods will be entered in each booklet.

If the patient is transferred to another hospital or department (hereinafter referred to as hospital transfer) during the observation period, the patient will be newly registered even at the transferred site and the CRF will be completed. If the patient is transferred to another hospital, the patient registration number of the original site will be conveyed to the transferred site. Although the patient will be given a new patient registration number at the transferred site at the time of registration, he or she will be determined to be a transferred patient by reporting the patient registration number of the original site and his/her data will be handled as the same patient. If the time point of 30 months after the start date of initial administration can be identified for the transferred patient, the observation period at the transferred site may be reset so that the total observation period of the patient in this study will become 30 months.

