6. ENDPOINTS AND COVARIATES

6.1. Safety Endpoints

- Adverse reactions: Adverse events assessed as related to this drug by the physician
- Adverse events: Adverse events of any causality
- Serious adverse events or adverse reactions: Adverse events or adverse reactions assessed as serious by the physician
- Safety specifications: Events to be handled as safety specifications will be specified according to the latest version of the “Rationale for Safety Specifications and Events to be Defined based on the Risk Management Plan.”
- Important potential risks:
 - Hepatotoxicity
 - Hypersensitivity reactions
 - Reproductive and developmental toxicity
 - Infection
 - Incorrect product selection between Vyndaqel and Vynmac
- Laboratory tests

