8.1.6. Analysis based on the person-years method

The incidence rate per exposure period will be calculated using the following formula:

$$\text{Incidence rate (per 100 person-years)} = 100 * y / PT$$

y: Number of patients with event

PT: Total exposure period (years)

Where the exposure period is the period from the first date of administration to the date of last observation in this study for patients with no event and the period from the first date of administration to the first date

of confirmation of the event in this study for patients with an event. The 95% confidence interval will be calculated using the following formula:

$$\left[\frac{100}{PT} \cdot \frac{1}{2} \chi^2_{2y} \left(\frac{\alpha}{2} \right), \frac{100}{PT} \cdot \frac{1}{2} \chi^2_{2(y+1)} \left(1 - \frac{\alpha}{2} \right) \right]$$

y: Number of events

$\chi^2_{2y}(\alpha/2)$: $\alpha/2$ percent point of the chi-square distribution with $2y$ degrees of freedom

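### The Vyndaqel/Vynmac mix-up risk is analysed over the whole safety set and without delayed entry, although no patient could experience it before Vynmac was approved in September 2021

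*SAP*

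**What the plan says.** SAP 6.1 lists "Incorrect product selection between Vyndaqel and Vynmac" among the important potential risks. The definition of the event is held elsewhere: "Events to be handled as safety specifications will be specified according to the latest version of the" separate document on the rationale for safety specifications.

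The analysis is in SAP 8.2.3.1.4: "For the safety specifications shown in Section 6.1, the number and proportion of patients will be tabulated". Protocol 8.7 divides by the number of patients in the safety analysis set (SAS) and applies the same method to the important potential risks. SAP 8.2.3.1.4 adds an analysis that allows for unequal exposure and refers it to SAP 8.1.4. That section gives Kaplan-Meier quartiles and plots; it states no time origin for this use and no delayed entry.

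The person-years method is in SAP 8.1.6, where exposure is "the period from the first date of administration to the date of last observation in this study for patients with no event" (or up to the first event). No analysis in SAP 8.2 cites 8.1.6.

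Three facts fix the calendar:
- Protocol 8.2.4: "Registration period: March 2019 to March 2021", running from the first patient's start of administration to the last patient's.
- Protocol 8.2.6: observation lasts 30 months (Week 130) from Day 1. For a patient who stops the drug, "the observation period will be until the first visit after the date of discontinuation".
- Protocol 6: "Vynmac was approved for marketing in September 2021 for ATTR-CM".

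**The concern.** Two products cannot be confused before the second one exists. Every surveyed patient began treatment before Vynmac was approved, so each has an initial stretch in which this event was impossible. Anyone who died, stopped or was lost before approval could never have had it. The other safety specifications can occur from Day 1, so the common denominator and time axis suit them. They do not suit this one, and the plan sets no separate rule for it.

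At stake is how the result for a named risk-management item is read. A low proportion or a low cumulative incidence could be taken as evidence that the two products are seldom confused, when part of it reflects time and patients not at risk. A curve on time since first dose would also suggest a risk that grows with duration of treatment, when only the calendar has moved.

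**Working it through.** **Plan's own figure.** The documents give no expected incidence for this risk. The one probability in Protocol 8.5.2 concerns hepatotoxicity: P(X ≥ 10) with n = 300 and p = 0.0588 is 0.984, which agrees with the stated 98% but does not bear on this point.

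**From the documents' dates alone.** The latest start is 31 March 2021 and the earliest possible approval day is 1 September 2021. The gap is 154 days, about 5 months, and it is longer for everyone else. A patient starting on 1 March 2019 reaches Week 130 (910 days) on 27 August 2021 and is never at risk.

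**Assumptions for size (not in the documents).** Starts are uniform from 26 March 2019 to 31 March 2021 (736 days). Follow-up is 30 months (2.5 years, 913 days). Loss through death, stopping or transfer is 0 to 30% per year at a constant rate. Vynmac becomes available on 1 September, 30 September or 31 December 2021.

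**1. Proportion.** With λ = −ln(1 − annual loss), and g1 and g2 the shortest and longest gaps in years from start to availability (longest capped at 2.5), the share of patients ever at risk is [exp(−λ·g1) − exp(−λ·g2)] / (λ × 736/365.25).

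For 30 September the gaps run from 183 days (0.501 years) to 919 days, so g2 = 2.5. At 30% loss, λ = 0.357 and the share is (0.836 − 0.410)/0.719 = 0.593, or 178 of 300.

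| Loss per year | Ever at risk, of 300 | 300 / number at risk |
|---|---|---|
| 0% | 298 | 1.01 |
| 10% | 255 | 1.18 |
| 20% | 215 | 1.40 |
| 30% | 178 | 1.69 |

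The ends of the range are:
- Availability on 1 September, no loss: the longest gap is 890 days, below 913, so all 300 are at risk and the factor is 1.0.
- Availability on 31 December, 30% loss: g1 = 275 days (0.753 years), the share is (0.765 − 0.410)/0.719 = 0.49, and the factor is about 2.

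**2. Kaplan-Meier from first dose (SAP 8.1.4 as cited).** Take availability on 30 September 2021, no loss, and an illustrative constant true rate of 5 per 100 person-years. Week 130 is 910/365.25 = 2.491 years.
- Mean gap: (919 + 183)/2 = 551 days. Share of time at risk: (910 − 551)/910 = 0.395.
- True 30-month incidence: 1 − exp(−0.05 × 2.491) = 11.7%.
- Displayed incidence: about 1 − exp(−0.05 × 2.491 × 0.395) = 4.8%.

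| Weeks on drug | Share of time at risk | Apparent rate per 100 person-years |
|---|---|---|
| 0–26 | 0% | 0 |
| 26–52 | 12% | 0.6 |
| 52–78 | 37% | 1.9 |
| 78–104 | 62% | 3.1 |
| 104–130 | 86% | 4.3 |

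The true rate after availability is constant, so the rise is produced by the calendar.

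**3. Person-years from first administration (only if SAP 8.1.6 was meant).** The factor is 1 / (share of person-time at risk).
- 30 September: shares of 0.396, 0.372, 0.346 and 0.316 at 0, 10, 20 and 30% loss give factors of 2.5, 2.7, 2.9 and 3.2.
- 1 September, no loss: mean gap (890 + 154)/2 = 522 days; share (913 − 522)/913 = 0.428; factor 2.3.
- 31 December: factors 3.3 (no loss) to 4.3 (30% loss).

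**Sensitivity to the start pattern.** With starts from 1 March 2019 that are uniform, front-loaded or back-loaded, availability in September 2021 and 0 to 30% loss, the person-years factor runs from 1.8 to 5.5. The proportion factor runs from 1.0 to 2.1.

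**The case against.** The strongest reply is that the plan does not do what a hasty reader might infer. Three stronger readings are tempting, and the documents support none of them.

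- *The event count is divided by exposure from Day 1.* SAP 8.2.3.1.4 cites 8.1.4, which divides nothing by person-time. The reference to unequal exposure suggests that 8.1.6 was intended but does not establish it, so the person-years factors are conditional.
- *The SAS proportion is wrong.* It is the protocol's stated descriptive measure and describes that set correctly. It falls short only as an estimate of risk among patients who could have the event, and with no early loss the shortfall is negligible. The study is non-confirmatory with no decision rule (SAP 4). In an example with 5 affected patients, 5/300 is 1.7% (exact 95% CI 0.5 to 3.8). With 212 at risk (20% loss, mid-September availability, starts from 1 March 2019) it is 2.4% (0.8 to 5.4), and the intervals largely overlap.
- *A table by onset period will show the false rise.* That table (SAP 8.2.3.1.3) is specified for adverse reactions, whereas safety specifications are broken down by action taken and outcome. The artefact belongs to the Kaplan-Meier output.

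It can also be said that SAP 8.2.2.2 tabulates treatment time before and after the first switch, and that SAP 8.2.3.3 evaluates adverse reactions by product. These give context but not the risk set: the pre-switch period contains time before approval, and the post-switch period omits unswitched patients, who could also be affected by a selection error.

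The event definition was not available for this review. No definition, however, allows confusion with a product that is not yet available.

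**Conclusion.** The point holds in a limited form. The dates alone show that no patient was at risk for at least about 5 months and that some may never have been. Neither the protocol nor the SAP restricts the denominator, the risk set or the time origin for this item.

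The size differs by output:
- The proportion understates risk among patients who could have the event by a factor of 1.0 to about 2, depending on early loss and on the date of availability.
- Kaplan-Meier from first dose understates cumulative incidence (4.8% against 11.7% in the illustration) and adds a spurious late rise.
- A person-years rate, only if 8.1.6 was intended, would be about 2.3 to 4.3 times too low under the base assumptions.

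The existence of the problem is secure. Its size is not, because start dates, loss rates and launch date are not given; a launch after approval would enlarge it. This is a change that should be made, confined to one safety specification.

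**What to change.** In SAP 8.2.3.1.4, for this safety specification only:
1. State the date on which Vynmac became available. The sponsor must supply it, since the documents give only the approval month.
2. Report the count over the patients still receiving either product on or after that date, and show this number at risk beside the SAS proportion.
3. Start person-time, or use Kaplan-Meier with delayed entry, from the later of first administration and that date.
4. Settle whether the section should cite 8.1.4 or 8.1.6.

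The other safety specifications stay as they are.

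The cost is about one sentence, one derived date per patient and a corrected or confirmed cross-reference. Drug name and treatment period are already collected (Protocol 8.3.2), so no new patient data are needed. The downside is a smaller denominator and a slightly wider interval for this one item.

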### 7.1. Safety specifications

Important Potential Risks: Hepatotoxicity, hypersensitivity reactions, reproductive and developmental toxicity, infection, incorrect product selection between Vyndaqel and Vynmac

Important Missing Information: Safety in patients with severe hepatic impairment, administration to patients with variants

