#### 8.3.5. Presence or absence of pregnancy during the observation period (only for female patients)

The presence or absence of pregnancy at the end point of observation period in each booklet (or until the first visit date after the date of discontinuation of this drug) should be recorded. If pregnancy is found during the observation period, the information should be collected separately from the CRF.

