#### 8.5. Study size

##### 8.5.1. Sample size

A total of 300 patients will be included in the safety analysis set (SAS).

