##### 8.5.2. Rationale

The number of patients with ATTR-CM in Japan is estimated to be approximately 750. Of these, the proportion of patients who actually received the definitive diagnosis and were prescribed with this drug was estimated to be approximately 40% (approximately 300 patients). As a result, the target sample size was set at 300 subjects from the viewpoint of feasibility. The target sample size of 300 subjects was comparable to the active drug group (264 patients) in the global phase 3 study, and from this point of view, it is considered possible to confirm the safety and effectiveness of the drug to some extent.

If the number of subjects in the SAS is 300, at least 10 subjects with hepatotoxicity can be observed with a probability of approximately 98%, assuming that the true incidence of hepatotoxicity with the lowest incidence based on Studies B3461028 and B3461045 is 5.88% for infections, hypersensitivity reactions, and hepatotoxicity, all of which are important potential risks that can be reviewed.

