##### 2. Method of analysis

- Analysis for safety evaluation

Events possibly related to this drug are considered as adverse drug reactions (ADRs). The number of patients with ADRs and the proportion  $[(\%): \text{number of patients with ADRs} / \text{number of patients included in the SAS}]$  will be calculated.

Based on the above method, important missing information and important potential risks will also be evaluated.

- Analysis for effectiveness evaluation

Time course of changes in the following items from the start of administration of this drug will be recognized.

- NYHA Functional Classification
- Cardiac biomarker values (NT-pro BNP, BNP, troponin I, and troponin T)

In addition, survival time analysis will be performed using survival information obtained up to 30 months after the start of administration.

- Subset analysis

The analysis by variant genotype and NYHA Functional Classification will be also performed for the above safety and effectiveness evaluations.

Also, the onset status of adverse reactions will be evaluated for each product (Vyndaqel or Vynmac) during the treatment period until the first switching to Vynmac for Vyndaqel and during the treatment period after the first switching to Vynmac for Vynmac.

Detailed methodology for summary and statistical analyses of data collected in this study will be documented in the SAP, which will be dated, filed and maintained by the Sponsor. The SAP may modify the plans outlined in the full protocol; any major modifications of primary endpoint definitions or their analyses would be reflected in a full protocol amendment.

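### Reproductive and developmental toxicity is planned as a proportion of the whole safety analysis set, so a zero can look reassuring when few or no pregnancies were exposed

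*SAP*

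**What the plan says.** Protocol 7.1 lists the risk with four others: "Important Potential Risks: Hepatotoxicity, hypersensitivity reactions, reproductive and developmental toxicity, infection, incorrect product selection between Vyndaqel and Vynmac". SAP 6.1 repeats the list and leaves the definition of the events to a separate document linked to the risk management plan, which is not among the documents reviewed.

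For the analysis, SAP 8.2.3.1.4 says "For the safety specifications shown in Section 6.1, the number and proportion of patients will be tabulated". It names no denominator for any individual risk and asks for no confidence interval. The denominator comes from Protocol 8.7, which divides patients with adverse drug reactions by patients in the safety analysis set and then adds: "Based on the above method, important missing information and important potential risks will also be evaluated".

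The study-size rationale (Protocol 8.5.2) treats the risks unequally. It names infections, hypersensitivity reactions and hepatotoxicity, "all of which are important potential risks that can be reviewed". Reproductive and developmental toxicity is not named there.

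Pregnancy information is collected by two routes:

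- **CRF field.** Protocol 8.3.5 asks, for female patients, for "The presence or absence of pregnancy at the end point of observation period in each booklet". If a pregnancy is found, "the information should be collected separately from the CRF".
- **Safety reporting.** Protocol 10.1 requires every exposure during pregnancy to be entered on the CRF and reported to the sponsor's safety group within 24 hours, with or without an adverse event. Protocol 10.4.3 extends this to partners' pregnancies and follows each pregnancy to its outcome.

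**The concern.** A proportion is informative only if the people in its denominator could have had the event. Harm to a pregnancy or a fetus can arise only where there was an exposed pregnancy, of a patient or of a male patient's partner. Dividing by all treated patients mixes two quantities: how often pregnancy occurs in this population, and how often an exposed pregnancy is harmed. If pregnancy is rare, the first drives the result towards zero whatever the second may be.

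The survey is a condition of approval, and its results feed the re-examination application and proper-use material (Protocol 7 and 11). A line reading 0/300 (0%) beside similar lines for hepatotoxicity or infection invites the same reading for all of them. For those risks the whole safety set is a sensible denominator; for this one it is not.

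**Working it through.** **1. The plan's own figure.** Inputs from Protocol 8.5.1 and 8.5.2: n = 300 and a true hepatotoxicity incidence of 5.88%. The rationale states that "at least 10 subjects with hepatotoxicity can be observed with a probability of approximately 98" per cent. Expected cases are 300 × 0.0588 = 17.64. The exact binomial probability P(X ≥ 10) is 0.984, so the figure is reproduced. It applies to risks for which all 300 patients count as exposed. No corresponding figure is given for reproductive and developmental toxicity.

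**2. What a zero implies under different denominators.** The SAP's interval for a proportion, where one is calculated, is the exact two-sided 95% interval (SAP 8.1.3). With no events among n, the upper limit is 1 − 0.025^(1/n).

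| Denominator | n | Upper limit |
|---|---|---|
| Whole safety set (target size) | 300 | 1.2% |
| Units at risk (assumed) | 15 | 21.8% |
| Units at risk (assumed) | 6 | 45.9% |
| Units at risk (assumed) | 5 | 52.2% |
| Units at risk (assumed) | 3 | 70.8% |
| Units at risk (assumed) | 1 | 97.5% |
| None at risk | 0 | no information |

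For example, 1 − 0.025^(1/300) = 0.0122 and 1 − 0.025^(1/5) = 0.522. The first row is a limit on risk per treated patient. When the unit is an exposed pregnancy, the later rows are limits on risk per exposed pregnancy, which is the quantity the safety specification is about.

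**3. What a single case implies.** One case over the safety set is 1/300 = 0.33% (exact interval 0.01% to 1.84%), whatever the number of exposed pregnancies. Over three it would be 33% (0.8% to 90.6%); over six, 17% (0.4% to 64.1%).

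**4. How small the group at risk might be.** The documents give no sex mix, no share of women of childbearing potential and no pregnancy count, so this step is illustrative only. Assume 5% to 30% of patients are female and 1% to 10% of those are of childbearing potential:

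- lowest: 300 × 0.05 × 0.01 = 0.15 women
- highest: 300 × 0.30 × 0.10 = 9 women

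Assume also a yearly pregnancy probability r of 2% to 5% over 30 months (2.5 years). The chance of no maternal pregnancy at all among m women is (1 − r)^(2.5m). It runs from 0.98^0.375 = 0.99 down to 0.95^22.5 = 0.32. Partner pregnancies are not covered by this calculation.

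**The case against.** The strongest reply is that the data route is sound, and largely it is. A reader might infer from Protocol 8.3.5 that pregnancy is seen only at the end of a booklet, that the information sits outside the CRF, or that pregnancies ending earlier drop out of the count. The documents do not support these readings. Presence or absence of pregnancy is a CRF item in both booklets (Table 1). Protocol 10.1 puts every such exposure on the CRF and on a 24-hour report. Protocol 10.4.3 covers partners and sends adverse pregnancy outcomes such as spontaneous abortion or congenital anomaly through serious-event reporting. Adverse events are collected throughout observation (Protocol 8.3.8). Partner pregnancies have no row of their own in Table 1 but fall under the 10.1 rule.

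It is also fair to say that the SAP already gives context. It tabulates sex, age and pregnancy status (8.2.2.1), adverse reactions by pregnancy status (8.2.3.3), and a listing of adverse reactions by safety specification (section 9). The study is declared non-confirmatory, and the 1.2% limit is not a planned output.

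This reply disposes of any claim about lost data. It does not change the denominator in the safety-specification table, and the pregnancy-status tables do not cover paternal exposure. The exposure-adjusted analysis promised in 8.2.3.1.4 does not help either. The section it cites (8.1.4, Kaplan-Meier) and the person-years method (8.1.6) are not restricted to exposed pregnancies. Nor does the SAP say whether cases known only from the exposure-during-pregnancy forms enter the numerator.

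**Conclusion.** The point stands as a minor one about the denominator and presentation. Under the rule in Protocol 8.7, zero cases give 0%, with an upper limit of 1.2% at the target size, and each affected patient adds 0.33 percentage points, however many pregnancies were exposed. On an at-risk denominator, a zero would leave upper limits from about 22% (15 at risk) to 97.5% (one at risk), or nothing to estimate. The counts at risk are assumptions. The conclusion that the planned proportion does not depend on them is not.

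It would go too far to say that the table will show 0%, or that the study cannot observe this risk. The sex and age mix is not given, the event definition is in a document not supplied, and reporting routes for exposed pregnancies exist. The supportable statement is that the table can show an uninformative 0%.

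There is also a loose end between two protocol sections. Section 8.3.5 sends pregnancy information outside the CRF, whereas 10.1 requires all such exposures on it. These should be reconciled so that it is clear which record supplies the count.

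**What to change.** In SAP 8.2.3.1.4, for this risk only, add text to this effect:

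- Cases are taken from the CRF and from the maternal and paternal exposure-during-pregnancy reports required by Protocol 10.1 and 10.4.3, with duplicates reconciled.
- Cases are shown over the number of reported exposed pregnancies, maternal and paternal separately.
- Reproductive events outside pregnancy are listed as case counts without a percentage.
- If there are no exposed pregnancies, the entry reads 'not evaluable' in place of 0%.

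The SAP already has precedents for both devices. SAP 8.2.3.1.3 sets a special denominator for time to onset, and 8.2.3.3 declines a tabulation on contraindications because the study cannot evaluate it properly.

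Also state how Protocol 8.3.5 and 10.1 fit together as the source of the count. Rewording the pregnancy question in 8.3.5 would gain nothing, because observation was planned to end in September 2023 (Protocol 5).

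The cost is a few lines of SAP text and a small reconciliation with the safety database, with no new data collection. One limitation should be stated in the report: the paternal denominator contains only the partner pregnancies that were reported.

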8.2.3. Safety analysis

All adverse reactions and adverse events occurring after the start of administration of this drug will be summarized in listings. The listings will include all events reported in this study. Safety will be evaluated using all data collected after the start of administration of this drug without classifying the data into Vyndaqel and Vynmac unless otherwise specified was added.

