9. LISTINGS

The following listings will be prepared:

- Listing of patients
- Listing of patients experiencing adverse events
- Listing of patients experiencing adverse reactions
- Listing of patients excluded from the safety analysis experiencing adverse reactions
- Listing of patients with a contraindication experiencing adverse reactions
- Listing of patients experiencing serious adverse reactions
- Listing of patients experiencing serious adverse events
- Listing of patients with TTR variants experiencing adverse reactions
- Listing of patients with severe liver impairment experiencing adverse reactions
- Listing of patients with renal impairment experiencing adverse reactions
- Listing of patients experiencing adverse reactions resulting in dose reduction
- Listing of pediatric patients (aged <15 years) experiencing adverse reactions
- Listing of elderly patients (aged ≥65 years) experiencing adverse reactions
- Listing of adverse reactions by safety specification
- Listing of laboratory test values
- Listing of efficacy evaluations

In addition, a form necessary for reexamination application (PSEHB/PED Notification No. 1128-2 dated November 28, 2017 issued by the Director of Pharmaceutical Evaluation Division, Pharmaceutical Safety and Environmental Health Bureau, Ministry of Health, Labour and Welfare) will be prepared.

Furthermore, a form necessary for Periodic Safety Update Reports (PSEHB/PED Notification No. 1128-5 and PSEHB/SD Notification No. 1128-4, dated November 28, 2017 issued jointly by the Director of Pharmaceutical Evaluation Division and the Director of Safety Division, Pharmaceutical Safety and Environmental Health Bureau, Ministry of Health, Labour and Welfare) will be prepared.

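### The counting rule stated for incorrect product selection (Vyndaqel/Vynmac) is built for adverse reactions, so a reported zero would be ambiguous

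*SAP*

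**What the plan says.** Both documents name the risk. Protocol 7.1 includes "incorrect product selection between Vyndaqel and Vynmac" among the important potential risks, and SAP 6.1 repeats it as a safety specification.

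**Counting rule.** Protocol 8.7 treats possibly related events as adverse drug reactions and divides the number of patients with them by the SAS. It then adds: "Based on the above method, important missing information and important potential risks will also be evaluated".

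**SAP table.** SAP 8.2.3.1.4 states: "For the safety specifications shown in Section 6.1, the number and proportion of patients will be tabulated". The sentence does not say that events must be related, but it stands under 8.2.3.1, Adverse reactions. The same section adds tables by action taken and outcome, and an analysis that allows for exposure period.

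**Event terms.** SAP 6.1 says: "Events to be handled as safety specifications will be specified according to the latest version of the" separate risk-management document, which is not among the documents available.

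**Listings.** The one listing in SAP 9 tied to these risks is "Listing of adverse reactions by safety specification". SAP 6.1 defines an adverse reaction as an AE that the physician judged related. For AEs and adverse reactions generally, SAP 8.2.3 says: "The listings will include all events reported in this study".

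**Capture.** The table in Protocol 10.1 requires medication errors to go on the CRF and to the sponsor's safety department within 24 hours, whether or not an AE occurred. Protocol 10.4.3 includes confusion over brand names, and also near misses that involve no patient.

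**The concern.** Hepatotoxicity, hypersensitivity and infection are clinical events, so asking whether the drug caused them makes sense. A product mix-up is a mistake in prescribing, dispensing or taking the drug. It may cause no AE at all, and if an AE follows, its relation to the drug does not decide whether the mistake happened.

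Under the stated rule, a mix-up with no AE, or with an AE judged unrelated, need not be counted. This risk entered the plan only because Vynmac was added. A table showing zero could be read as evidence that the two products are not confused, when it might show only that no mix-up led to a related AE.

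The denominator is a second, smaller matter. Registration ran from March 2019 to March 2021 (Protocol 8.2.4), and Vynmac was approved in September 2021 (Protocol 6). SAS patients who stopped before then could not have had this error.

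**Working it through.** **1. The plan's own precision figure.** Protocol 8.5.2 gives about a 98% chance of at least 10 hepatotoxicity cases with n = 300 and incidence 5.88%. The binomial tail P(X ≥ 10) is 0.984, so the figure reproduces. It is the only such figure in the documents and does not concern product selection.

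**2. Following a mix-up through the plan as written.**

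| Mix-up | Recorded or reported (Protocol 10.1, 10.4.3) | Counted under the Protocol 8.7 rule | In the SAP 9 listing for these risks |
|---|---|---|---|
| No AE | Required | Not required | Not required |
| AE judged unrelated | Required | Not required | Not required |
| Related AE | Required | Yes, if the terms in the separate document cover it | Yes, on the same condition |

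Only the last row is sure of a place under the stated rule. An error entered as an AE would also reach the general AE listings. Protocol 8.3.8 and Table 1 show no separate item for an error without an AE, though they are variable lists and not the CRF itself.

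**3. How much the numerator rule could matter.** The documents give no mix-up rate, no number at risk and no share of mix-ups recorded as related events, so all three are assumed. Let m be the patients at risk, e the true mix-up rate and q the share recorded as related events. The chance of a reported zero is (1 − e·q)^m. With e = 2%:

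| m | Every mix-up counted (q = 1) | q = 0.2 | q = 0.1 |
|---|---|---|---|
| 300 | 0.2% | 30.0% | 54.8% |
| 150 | 4.8% | 54.8% | 74.1% |

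For example, with m = 150 and q = 0.2: (1 − 0.02 × 0.2)^150 = 0.996^150 = 0.548. This illustrates the mechanism and is not an estimate for this study.

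**4. The denominator.** Assume starts spread evenly from March 2019 to March 2021, that is 30 to 6 months before approval, and a constant annual discontinuation p (assumed, since none is given). The expected number on treatment at approval is 300 × the mean of (1 − p)^(s/12), with s uniform on 6 to 30 months. For p < 1 and p ≠ 0 that mean is [(1 − p)^0.5 − (1 − p)^2.5] / [−2 ln(1 − p)]. The exact two-sided 95% upper limit for 0 of n is 1 − 0.025^(1/n).

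| p | Expected on treatment | n | Upper limit for zero cases |
|---|---|---|---|
| 0% | 300 | 300 | 1.22% |
| 10% | 256.6 | 257 | 1.43% |
| 20% | 216.4 | 216 | 1.69% |
| 30% | 179.4 | 179 | 2.04% |

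SAP 8.2.3.1.4 does not ask for an interval. The limits only show how much a zero would tell. Patients who started in March 2019 reached 30 months at about the approval date, so even the p = 0% row slightly overstates the number at risk.

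**The case against.** The strongest objection is that the event definitions sit in a document not seen here. It may name medication-error terms and may say that causality is irrelevant. The SAP sentence does not say related, and Protocol 8.7 lets the SAP modify the protocol's outline. This stands as a limit on certainty. But naming terms would not by itself set aside the related-event rule or choose a denominator, and neither available document does so for this risk.

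Some stronger readings are tempting but not supported:

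- **Mix-ups go unrecorded.** Protocol 10.1 and 10.4.3 require them to be recorded and reported regardless of AE. The gap is in counting, not in capture.
- **The SAP restricts the table to related events and has no other analysis.** Its sentence has no such restriction, and the section adds an analysis allowing for exposure period. That analysis does not settle the point, because neither it nor SAP 8.1.4 states a causality rule or a group at risk for this error.
- **Readers cannot see how many patients received Vynmac.** SAP 8.2.2.2 tabulates the Vynmac treatment period after the first switch, and SAP 8.1.1 includes the number of patients. This is not the same as the number on either product while both could be confused, but it is informative.
- **A single case would be dropped by the AE threshold.** One case in 300 is 0.33%, so a higher cut-off would remove it from the non-serious AE table. But SAP 8.2.3.2.1 sets a threshold only if needed and gives no value, and it does not apply to the safety-specification table or to the listings.

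It is also fair to say that the study is descriptive (SAP 4) and that risk-management review draws on more than one table (Protocol 13 and 14). That lowers the stakes but does not make a zero easier to interpret.

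**Conclusion.** The point holds as a mismatch between a medication-error risk and a counting rule made for adverse reactions. Followed as written, the plan need not count a mix-up without a related AE, although the protocol demands that such a mix-up be recorded.

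The size of any undercount is unknown. The illustrative chances of a reported zero rest wholly on assumed rates. The denominator effect is modest: an upper limit for zero cases of about 1.2% to 2.0%, under even entry and assumed annual discontinuation of 0% to 30%. The numerator is the part that matters.

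Confidence is medium, because the separate document could contain a suitable rule. If it does, the remedy is to state that rule in the SAP. This is an improvement worth making and does not affect the study's other results.

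**What to change.** Add to SAP 8.2.3.1.4, for incorrect product selection only:

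- **Numerator:** SAS patients with any recorded incorrect product selection involving exposure, regardless of AE or causality. The sources are CRF entries reconciled with the 24-hour medication-error reports.
- **Subset:** of these, the patients with a related AE, shown separately.
- **Near misses without a patient:** listed separately and kept out of the proportion.
- **Denominator:** SAS patients still on treatment and under observation on or after the date Vynmac became available, with that number shown. The documents give only the approval month, so use September 2021 if the availability date is not fixed.
- **Interval:** the exact two-sided 95% interval of SAP 8.1.3.

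The cost is a few lines of SAP text and one extra table. The 24-hour reports reach the safety department separately from the CRF, so some matching by patient is needed, and possibly some queries. No new patients are needed, and the other analyses are unchanged.
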